a. Hyperinsulinemic-euglycemic clamp procedure. At ~0700h in the morning after admission, after subjects have fasted for ~11 hours overnight, an intravenous catheter will be inserted into an antecubital vein to infuse stable isotope tracers, insulin and dextrose. A second catheter will be inserted into a radial artery to obtain arterial blood samples. A primed-constant infusion of [6,6-²H₂]glucose and a constant infusion of [U-¹³C]palmitate will be started and maintained for 3.5 h to obtain basal glucose and fatty acid kinetics. At ~1030h, insulin will be infused for ~3.5 h at 50 mU/m² BSA/min (initiated with a two-step priming dose of 200 mU/m² BSA/min for 5 min followed by 100 mU/m² BSA/min for 5 minutes). Euglycemia (~100 mg/dL) will be maintained by variable rate infusion of 20% dextrose enriched to 2.5% with [6,6-²H₂]glucose. Adding glucose tracer to the dextrose infusion provides a more accurate measure of glucose kinetics by minimizing changes in plasma glucose enrichment [35]. The infusion rates of [6,6-²H₂]glucose and [U-¹³C]palmitate will be decreased by 75% during insulin infusion, because of the expected decreases in endogenous glucose production and palmitate release into the circulation. Blood samples will be obtained immediately before starting the tracer infusion and every 10 min during the final 30 min (4 samples) of the basal period and clamp procedure, to determine glucose and insulin concentrations and substrate kinetics. We have found this infusion protocol is well-tolerated by study subjects and is needed to achieve steady-state conditions in plasma glucose tracer enrichment during each stage.

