c. NMN pharmacokinetics. NMN concentration or NMN metabolites in plasma, and NAD⁺ concentration in PBMCs, muscle and adipose tissue will be obtained at baseline and after 16 weeks of placebo or NMN treatment. Blood for plasma NMN, PBMC, muscle and adipose tissue will be obtained 60 minutes after

ingesting placebo or NMN capsules during the basal period of the hyperinsulinemic-euglycemic clamp procedure performed after 16-week treatment period.

d. Arginine stimulation test. After completing the hyperinsulinemic-euglycemic clamp procedure, an Arginine bolus infusion will be given over 1 minute, followed by blood sampling every 2 min for 10 min to assess maximal β -cell function.

Sleep monitoring. Wrist actigraphy with concurrent light exposure (Actiwatch Spectrum Pro; Philips Respironics) will be used to assess total sleep time during the 7-10 day period before and after 16 weeks of treatment period. Participant will also be asked to complete a sleep journal during this monitoring period.

Sleep questionnaire. Participants will be asked to take answer a questionnaire about their sleep quality.

C.3.2.2. Baseline Visit 2

a. Body composition analyses. In the afternoon of admission, intra-abdominal adipose tissue volume, intrahepatic triglyceride content, and liver fibrosis will be assessed by magnetic resonance imaging (MRI) and magnetic resonance elastography (MRE) [34]. These tests might be scheduled on different days as separate visits or in combination with another visit if necessary.

If a participant has claustrophobia, they will be given the option of taking a benzodiazepine (Ativan or Xanax) pre-procedure which will be dispensed through BJC Pharmacy. If a participant does agree to take the benzodiazepine, prior to the prescription his/her medical history will be reviewed by a study physician. If a participant does take a benzodiazepine during MRI scan, he/she will be required to have a ride home by a caregiver after the visit and to avoid alcohol or other sedating agents overnight.

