a. Substrate kinetics and insulin sensitivity. Glucose and palmitate kinetics during the clamp procedure will be used to provide an index of hepatic, skeletal muscle and adipose tissue insulin sensitivity, as we previously described [31, 38, 39]. Glucose Ra in plasma during basal conditions and the clamp procedure will be calculated by dividing the glucose tracer infusion rate by the average plasma glucose TTR during the last 30 min of the basal and clamp periods, respectively. Glucose Ra during basal conditions represents endogenous glucose Ra, an index of hepatic glucose production rate, which equals basal glucose rate of disappearance (Rd). During the clamp procedure, hepatic glucose production rate will be calculated by subtracting the glucose infusion rate (i.e., dextrose solution plus tracer added to it) from total glucose Ra (endogenous plus exogenous); glucose Rd is equal to total glucose Ra (i.e., the sum of endogenous glucose Ra and the rate of infused glucose). Palmitate Ra, an index of adipose tissue lipolysis will be calculated by dividing the palmitate tracer infusion rate by the average plasma palmitate TTR obtained during the final 30 min of the basal period and insulin infusion.

b. β -cell function. Insulin secretion rate (ISR) during the modified 3-h oral glucose tolerance test (MOGTT) will be calculated by stochastic deconvolution analysis of the plasma C-peptide concentration time-course [40]. β -cell response sensitivity to glucose will be assessed as the ratio of the area under the curve (AUC) of ISR (pmol/L) to the AUC of glucose [41-43]. β -cell function in relation to insulin sensitivity will be assessed based on the principle of the disposition index, calculated as the product of the area under the curve (AUC) of ISR (pmol/L) assessed during the MOGTT and the rate of insulin-stimulated glucose disposal normalized for plasma insulin concentration ($\mu\text{mol/kg FFM/min per } \mu\text{IU/mL}$) assessed during the hyperinsulinemic euglycemic clamp procedure, as we have previously reported [20]. Insulin secretory reserve will be assessed by measuring the AUC of insulin and ISR over 10 min after the intravenous administration of 5 g of arginine [44, 45].

C.3.9. Sample analyses.

All sample analyses are routinely performed by our research group or in our Core laboratories at Washington University School of Medicine.

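### One of the two arginine-test readouts of insulin secretory reserve, the plasma insulin AUC, includes residual insulin from the preceding clamp, and the plan specifies no correction

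*Combined protocol and SAP*

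**What the plan says.** The arginine test is part of β-cell function, a secondary outcome (C.3.1.b.ii). Four places in the protocol bear on it.

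- **Clamp (C.3.2.1.a).** From about 1030 h, "insulin will be infused for ~3.5 h at 50 mU/m² BSA/min", after a two-step prime. Samples in the last 30 min of the basal period and of the clamp are taken "to determine glucose and insulin concentrations and substrate kinetics". C-peptide is not named.
- **Arginine test (C.3.2.1.d).** "After completing the hyperinsulinemic-euglycemic clamp procedure, an Arginine bolus infusion will be given over 1 minute". Blood is then drawn at 2-min intervals over 10 min as a test of maximal β-cell function. The section gives no interval between clamp and bolus and does not say whether the insulin infusion has stopped. It mentions no sample just before the bolus and lists no analytes.
- **Calculation (C.3.8.b).** Secretory reserve is "assessed by measuring the AUC of insulin and ISR over 10 min after the intravenous administration of 5 g of arginine". Two quantities are scored and neither is named as the main one. No incremental AUC is defined.
- **ISR (C.3.8.b).** ISR is obtained by deconvolution of plasma C-peptide, but this is described only for the oral glucose tolerance test.

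**The concern.** Secretory reserve is meant to describe what the β-cell releases. Plasma insulin measured soon after an insulin infusion is the sum of infused and secreted hormone, and the plan names no assay that tells them apart. Residual infused insulin depends on how fast the participant clears insulin and on how long the infusion has been off. Neither is secretion.

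Two things are at stake. First, a difference in clearance or in timing, between participants, visits or arms, could be read as a difference in reserve. The plan itself expects insulin levels to differ at a fixed infusion rate, because C.3.8.b normalizes clamp glucose disposal for plasma insulin concentration. Second, if the insulin AUC and ISR disagree, the plan does not say which one counts.

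**Working it through.** The documents give no figure for this outcome, so there is none to reproduce. The check estimates how much of the 10-min insulin AUC would be infused insulin.

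**Input from the protocol:** infusion rate 50 mU/m²/min (C.3.2.1.a); AUC window 10 min (C.3.8.b).

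**Assumptions, not in the documents:** insulin clearance 0.4 to 0.7 L/m²/min; plasma half-life 4 to 6 min with single-exponential decay; mean endogenous level over the window 20 to 60 µU/mL, which is an AUC of 200 to 600 µU·min/mL.

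**Formulas**
- Infused insulin at clamp end: C = 50 / clearance, which gives 50/0.7 = 71 to 50/0.4 = 125 µU/mL.
- Infusion continues: infused AUC = 10 × C.
- Infusion stopped d minutes before the bolus: infused AUC = C × exp(−kd) × (1 − exp(−10k)) / k, with k = ln 2 / half-life.
- Share = infused AUC / (infused AUC + endogenous AUC).

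**Results**

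| Infusion status | Infused AUC (µU·min/mL) | Lowest share | Highest share |
|---|---|---|---|
| Continues through the window | 714 to 1250 | 714/(714+600) = 54% | 1250/(1250+200) = 86% |
| Stops at the bolus | 339 to 741 | 339/(339+600) = 36% | 741/(741+200) = 79% |
| Stopped 15 min before | 25 to 131 | 25/(25+600) = 4% | 131/(131+200) = 40% |
| Stopped 30 min before | 2 to 23 | 2/(2+600) = 0.3% | 23/(23+200) = 10% |

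A larger endogenous response lowers every share. At a mean of 100 µU/mL (AUC 1000), the range is 339/1339 = 25% to 741/1741 = 43% if the infusion stops at the bolus, and 714/1714 = 42% to 1250/2250 = 56% if it continues.

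**Sensitivity to the interval.** Take C = 100 µU/mL and a 5-min half-life. The infused AUC is 541 with no gap and 68 after 15 min. A gap that differs by 15 min between two tests would then move the insulin AUC by 541 − 68 = 473 µU·min/mL with no change in secretion. That lies within the assumed range for the whole endogenous response (200 to 600).

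**The case against.** The strongest reply is that C.3.8.b already lists ISR beside the insulin AUC, and C-peptide-based ISR contains no infused insulin. That stands: the outcome as a whole is not invalid. What remains is that both readouts are scored without ranking, and that C-peptide sampling in the arginine test is implied by the word ISR but not specified.

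A reader might infer that arginine is given immediately after the clamp. Insulin from about 1030 h for about 3.5 h ends near 1400 h, which is also when a stay of about 24 h from about 1400 h would end. All of these times are approximate. Read strictly, they would leave no time even for the arginine test itself. C.3.2 also lets timing and order vary for convenience. The documents leave the interval unspecified; they do not establish that it is zero.

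A reader might also infer that the insulin AUC mostly measures infused insulin. That depends on the unstated interval and infusion status and on values from outside the documents. It fails after a gap of 15 to 30 min, and under some assumptions it fails with no gap at all.

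Nor do the documents show bias between arms. The infusion rate per m² is the same in both, so bias would need an effect of NMN on insulin clearance or unequal gaps, and the documents give evidence of neither. The ANCOVA in Section D adjusts for the pre-intervention value, which would remove part of any stable difference in clearance between participants. On the absolute scale, added insulin unrelated to treatment increases variance but does not shrink the difference between arms. It shrinks percentage or log-scale effects, and Section D allows log transformation of skewed variables.

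**Conclusion.** The concern holds for one of two readouts of a secondary outcome. As written, the insulin AUC mixes residual infused insulin with secreted insulin and varies with clearance and with an interval that the plan does not fix or record. Under the stated assumptions the infused part ranges from negligible, about 10% or less with a 30-min gap, to dominant, 54 to 86% with the infusion running. The documents do not say where in that range the trial falls. This is more than missing detail, because a site that follows the text exactly would still score a contaminated measure as secretion. ISR is not affected. The primary outcome, insulin-mediated glucose Rd, is not affected either, nor is the sample size, which Section D bases on that outcome alone. The change should be made, but the trial's main conclusion does not depend on it.

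**What to change.** In C.3.8.b, define secretory reserve solely as the AUC of C-peptide-based ISR over 0 to 10 min after arginine, incremental to the pre-arginine ISR. Drop the insulin AUC, or keep it labelled as descriptive only.

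In C.3.2.1, specify C-peptide assay in the arginine samples and in the final clamp samples that are already drawn. Several clamp samples serve better than one, because ISR is deconvolved from a time course. If there is a gap after the clamp, add a sample immediately before the bolus, so that the baseline is a true pre-arginine value.

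State the insulin infusion status at the bolus, and record it together with the clamp-to-arginine interval at both the baseline and the repeat test.

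The cost is one revised definition, a few extra C-peptide assays, at most one further blood sample where there is a gap, and one readout fewer. No new participant procedure is needed.

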Statistical evaluation of the study data will be carried out in collaboration with [name], who is an applied biostatistician with expertise in the design and analysis of clinical trials. Our primary analysis will be intention-to-treat in people with prediabetes. Preliminary analyses involving t-tests or Wilcoxon's test for continuous variables and chi square tests for dichotomous variables will be performed to confirm that baseline characteristics of subjects are similar in the placebo and NMN treatment groups. ANCOVA with the post-treatment value of the metabolic outcome measure (e.g., our primary outcome variable is insulin-mediated glucose uptake) as the dependent variable will be used to determine whether there are between group differences in the outcome measure after adjusting for the pre-intervention value and any measures that were significantly different before or during the intervention. We will explore the distributional properties of the metabolites; if the variables are skewed, we will analyze the data following a data transformation (e.g., a log transformation). If an appropriate transformation cannot be found, we will analyze the data semi-parametrically by using the ranks of the data. An exploratory goal of this study is motivated by preliminary data from rodents suggesting that the efficacy of NMN on the primary outcome may be greater in female than male animals. Therefore, we will evaluate the interaction between sex and treatment group by using analyses of covariance. These analyses should provide evidence regarding the possibility that efficacy differs according to the sex of the individual. We emphasize the exploratory nature of these analyses. This study is not powered to evaluate the relevant interaction term, and our purpose is to generate preliminary data to determine whether a subsequent larger study to assess the response to NMN based on sex is worthwhile.

Sample size considerations. The single primary endpoint in this study is insulin-mediated glucose Rd. All other endpoints are secondary. Because there is only one primary endpoint, the power computations for that endpoint are not adjusted for multiple testing. We also present power computations for important secondary endpoints below, but emphasize that the target sample size is based on considerations related to the primary outcome only.

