Using G*Power 3.1.9.2 and day-to-day variance we have previously reported in similar intervention studies [38, 60], we estimated that 22 participants/group will be needed to detect *realistic and physiologically and clinically meaningful* between-group differences in insulin-mediated glucose Rd [61, 62] with >90% power using a two-sided test and an α value of 0.05 in all primary outcomes listed below. Therefore, we will enroll 28 participants

in each group to ensure that an adequate number of participants complete the study (allowing for an estimated 6 drop-outs/group). All of the power computations below are based on a power of 0.9.

Insulin-mediated glucose Rd. We have reported day-to-day variability in insulin-mediated glucose Rd during high-dose insulin infusion (means \pm SD) to be 3.4 ± 6.1 $\mu\text{mol/kg FFM/min}$ in people with prediabetes. Using these SDs and assuming similar variance in the placebo and NMN groups, we estimate we will be able to detect a ~ 6.2 $\mu\text{mol/kg FFM/min}$ difference between groups in subjects with prediabetes ($\sim 14\%$ difference based on an expected mean glucose Rd at baseline of 44.5 $\mu\text{mol/kg FFM/min}$) [61].

Tissue gene expression. It is difficult to make robust estimates of our study power to detect changes in the molecular outcomes in adipose tissue and muscle, because of limited data evaluating these variables and the unknown effects of altering sleep. However, in our own experience, the day-to-day variance in muscle and adipose tissue gene expression is $\sim 30\%$ [52]. Accordingly, we estimate that we have $\geq 90\%$ power to detect statistically significant effect of NMN therapy in both people with prediabetes, if the differences from placebo are $>30.5\%$. Our previously published data [61] indicate that differences in adipose tissue gene expression of this magnitude are *realistic* in response to dietary and pharmacological intervention. Our study also has other (secondary) outcomes listed in Section C.3.1.b. These outcomes are important and we believe they will generate important information. However, it is difficult to estimate statistical power for these outcomes because of inadequate available information.

E. Retention and Recidivism plan.

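### Baseline significance tests cannot show that the arms are similar, and letting them choose ANCOVA covariates leaves the primary model unfixed, with a conditional cost in power

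*Combined protocol and SAP*

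**What the plan says.** Section D (Statistical plan and Data analysis) plans preliminary t-tests or Wilcoxon tests for continuous variables and chi-square tests for dichotomous ones. These "will be performed to confirm that baseline characteristics of subjects are similar in the placebo and NMN treatment groups". The next sentence defines the ANCOVA for the post-treatment outcome, with insulin-mediated glucose uptake as the primary variable, as "adjusting for the pre-intervention value and any measures that were significantly different before or during the intervention".

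The section gives no margin for similarity, no significance threshold for these tests, no list of candidate measures and no limit on how many may enter.

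Under Sample size considerations, "we estimated that 22 participants/group will be needed to detect" the target difference "with >90% power using a two-sided test", and 28 per group are enrolled to allow for 6 drop-outs. No allowance is made for extra covariates. Section C.3.3 stratifies randomisation by BMI (two strata) and sex. Section D does not name either as a covariate in the primary model; sex appears only in an exploratory interaction with treatment.

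**The concern.** There are two faults.

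First, the tests cannot do what is asked of them. Their null hypothesis is that both arms come from one population. Randomisation makes that true by design, so a rejection is a chance event. A non-rejection only says that the observed gap was smaller than the sampling threshold, which is wide at this sample size.

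Second, the result is acted on. A measure enters the primary model because it happens to be imbalanced, whether or not it predicts glucose Rd. A prognostic measure with moderate imbalance stays out. The measures admitted are, by construction, those most correlated with treatment, so they inflate the standard error of the treatment effect. BMI stratum and sex would rarely enter, because stratification makes a significant difference in them unlikely.

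At stake are the pre-specification of the only primary analysis and, under some conditions, a few points of power. The text does not say outright that the baseline tests are the ones that trigger adjustment, but for measures differing before the intervention that is the natural reading.

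The same clause also admits measures that differ during the intervention. These are post-randomisation variables, and adjusting for one that treatment affects can bias the estimate.

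**Working it through.** **Inputs from section D:** SD 6.1 and difference 6.2 µmol/kg FFM/min, two-sided α 0.05, 22 completers and 28 enrolled per group. **Assumed, because the documents do not say:** baseline tests at two-sided 0.05; 5 to 30 candidate measures (section C.3.1 lists many that could qualify); their correlations and prognostic strength; 6.1 as the residual SD after baseline adjustment; baseline Rd SD of 10 in the simulation.

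**1. The plan's own figure.** d = 6.2/6.1 = 1.016 and noncentrality = d·√(n/2). The exact two-sample t-test has power 0.895 at 21, 0.909 at 22 and 0.962 at 28 per group. The stated 22 reproduces, with under one point to spare above 90%.

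**2. What passes as similar.** The smallest observed difference reaching p < 0.05, in SD units, is t(0.975, 2n−2)·√(2/n).
- 28 per group: 2.005 × 0.267 = 0.54 SD
- 22 per group: 2.018 × 0.302 = 0.61 SD

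Baseline testing precedes randomisation (C.3.3), so 28 per group is the planned case.

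**3. How often the rule fires.** With k independent candidates, the chance of at least one flag is 1 − 0.95^k: 23% for 5, 40% for 10, 64% for 20 and 79% for 30.

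**4. Cost of one just-significant covariate.** Variance inflation is 1 + t²/(2n−2). At 22 per group this is 1 + 2.018²/42 = 1.10; at 28 it is 1 + 2.005²/54 = 1.07. The variance of the treatment effect is multiplied by inflation × (1 − R²), where R² is the share of residual variance that the covariate explains.
- At 22 per group, against 0.908 with baseline Rd alone: 0.881 at R² = 0, 0.897 at 0.05, 0.912 at 0.10, 0.940 at 0.20. Break-even is 1 − 1/1.097, about 9%.
- At 28 per group, R² = 0: 0.950.

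**5. Average power of the whole rule, by simulation.** Post-treatment Rd was generated as baseline plus effect plus a normal change with SD 6.1. Any candidate with t-test p < 0.05 was added to an ANCOVA already containing baseline Rd. Each setting had at least 3,000 trials, so the simulation error is about half a point. Baseline Rd alone gave 0.90–0.91 at 22 per group and about 0.96 at 28.

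| Candidates | Rule, 22/group | Rule, 28/group |
|---|---|---|
| 5, non-prognostic | about 0.89 | 0.95–0.96 |
| 10, non-prognostic | 0.87–0.88 | 0.94–0.95 |
| 20, non-prognostic | 0.85–0.87 | 0.93–0.94 |
| 30, non-prognostic | about 0.84–0.85 (runs spanned 0.83–0.87) | 0.92–0.94 |
| 5, jointly explaining 20% of residual variance | 0.90–0.91 | about 0.96 |
| 10, jointly explaining 20% | about 0.89 | 0.95–0.96 |

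With no treatment effect, the rejection rate under the rule was 0.038–0.057.

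**6. The fixed model.** At 22 per group, adding BMI stratum and sex as non-prognostic covariates gave 0.900 against 0.901 when stratification held them balanced. Two non-prognostic covariates left to chance imbalance gave 0.883.

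**The case against.** A reader might infer three stronger things, and the documents support none of them.

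- *That the tests miss a real half-SD difference 55% of the time at 28 per group, or 63% at 22.* The arithmetic is right (power 0.451 and 0.367). But randomised arms have no true baseline difference to miss, the half-SD margin is not in the plan, and 63% would apply only if completers alone were tested. The observed-imbalance threshold in step 2 is the relevant figure.
- *That the rule takes power below the stated level.* This needs the full loss of 6 per group, together with candidates that are many or weakly prognostic. If everyone completes, average power stayed above 90% in every setting. The starting margin is also under one point, so almost any added non-prognostic covariate crosses 90%.
- *That the baseline trigger biases the result or inflates false positives.* The rejection rate stays near 5%, and no bias is shown for this half of the clause.

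It can also be said that pre-specification does not by itself gain power. Three fixed non-prognostic covariates gave 0.87–0.88 at 22 per group, no better than the rule with 10 candidates. That is correct, and it is why the fix uses only the factors the design already singles out. Baseline testing is also a common convention. None of this answers the two central faults: non-significance is not evidence of similarity, and the covariates of the primary analysis are left to chance.

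**Conclusion.** The point holds as a fault of method with a modest, conditional cost. It rests on the plan's stated rule and not on missing detail. The similarity claim is unsupported, since imbalances up to about 0.54 SD pass at 28 per group. The primary model is not fixed in advance, so two analysts could follow the text and fit different models.

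At the plan's own completer number, the average loss runs from about 1 point with 5 non-prognostic candidates to about 5 or 6 with 30. It is about one point or nil with 5–10 candidates that jointly explain 20% of residual variance. With no drop-out the power claim survives. These sizes depend on the assumed number, correlation and prognostic strength of the candidates. The two central faults do not. The change should be made before unblinding.

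**What to change.** In section D:

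1. Delete the baseline hypothesis tests and the statement that they confirm similarity. Report baseline characteristics by arm descriptively, with standardised differences and no p-values.
2. Replace "adjusting for the pre-intervention value and any measures that were significantly different before or during the intervention" with one fixed primary model: post-treatment Rd on treatment, baseline Rd, BMI stratum and sex, used whatever imbalance is observed.
3. Remove the during-intervention half together with the before half. Leaving it in would keep the model data-driven and would keep adjustment for variables that treatment may affect.
4. Put any adjustment for other imbalanced baseline measures into a labelled sensitivity analysis.

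The cost is a few sentences, with no new data, visits or participants. Each added covariate uses one degree of freedom. If BMI stratum and sex prove non-prognostic, the loss at 22 per group is at most about 1–2 points, and close to nothing where stratification keeps them balanced. Chance imbalance in an unlisted measure is then addressed only in the sensitivity analysis.

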Effect of NMN Supplementation on Organ System Biology
NCT NCT04571008
Date: May 15, 2023

Table of Contents

STUDY TEAM.....	3
OVERVIEW OF THE STUDY	3
A. Background and Significance	4
B. Objectives/Specific Aims/Hypotheses	6
C. Study Design	7
D. Statistical plan and Data analysis.....	14
E. Retention and Recidivism plan.	15
F. Timeline.	15
G. Foreseeable Risks or Discomforts	15
H. Protect Against Risk	18
I. References.....	19

STUDY TEAM

Principal Investigator: [name].
Washington University School of Medicine in St. Louis
[name]
[name]
[name]
[contact]
e-mail address: [contact]

Co-Investigators: [name].
[name].
[name]., Ph.D.

OVERVIEW OF THE STUDY

Study Title

Effect of NMN Supplementation on Organ System Biology

Objectives

To determine the effect of NMN supplementation on key health outcomes

Design and Outcomes

This study is a 16-week, randomized, placebo-controlled, double-blind trial to evaluate the efficacy of NMN supplementation on cardiometabolic function in middle-aged and older adult men and women who are overweight or obese and have evidence of metabolic dysfunction.

A total of 56 men and women will be enrolled and randomized to one of the study groups 1) Placebo (n=28) or 2) NMN supplementation (n=28). Men and women will be randomized separately to ensure number of men and women are similar in both groups.

This research study will be conducted at Washington University School of Medicine (WUSM) with weekly check-ins via phone or in person during the 16-week intervention.

[figure not shown]
- 1. Screening.** All participants will undergo a comprehensive outpatient screening visit, including review of medical history and blood tests, to determine eligibility for the study. Participants who meet the inclusion criteria will be admitted to the Clinical Translational Research Unit to complete baseline metabolic studies.

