b. NMN pharmacokinetics after the first dose of NMN. After subjects complete all baseline metabolic testing, NMN concentration or NMN metabolites in plasma and NAD⁺ concentration in PBMCs will be analyzed. Blood samples will be obtained before and 10, 20, and 60 minutes after the first dose of placebo or NMN.

c. Stool sample collection. Subjects will bring a frozen stool sample (obtained from home within 36 h of the study visit) by using a stool collection kit dispensed by the study coordinator during Visits 1 or 2.

C.3.3. Randomization procedure. After participants complete baseline metabolic testing, they will be randomly assigned to one of two groups: 1) placebo (two or three study pills made from food grade starch) once a day with breakfast for at least 16 weeks or 2) NMN (300 mg or 450 mg) once a day with breakfast for at least 16 weeks. A randomization scheme stratified by BMI (two strata: 25.0 kg/m² to 34.9 kg/m², and 35.0 kg/m² to 50.0 kg/m²) and sex (men and women) will be generated by using the randomization module of Research Electronic Data Capture (REDCap), a secure, web-based application designed to support data capture for research studies [37] and a randomization scheme to account for the potential imbalance in randomization. The study will be conducted in a double-blind fashion and both the participants and members of the research team directly involved with study participants and data analysis will be blinded to group assignment. An individual from the Washington University Center for Human Nutrition, who is not directly involved with the study participants and data analysis, will have access to a master list to unblind participants, if necessary.

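### The stratification factors, sex and BMI group, are not prespecified covariates in the primary ANCOVA; if they predict glucose Rd beyond its baseline value, precision is lost

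*Combined protocol and SAP*

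**What the plan says.** Section C.3.3 provides for "A randomization scheme stratified by BMI", with strata of 25.0 to 34.9 and 35.0 to 50.0 kg/m², "and sex (men and women) will be generated by using the randomization module" of REDCap. It gives no block size or balancing method, only "a randomization scheme to account for the potential imbalance in randomization". The overview (Design and Outcomes) mentions sex alone: "Men and women will be randomized separately to ensure number of men and women are similar in both groups".

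Section D gives the primary analysis as an "ANCOVA with the post-treatment value of the metabolic outcome measure" as dependent variable, comparing the groups "after adjusting for the pre-intervention value and any measures that were significantly different before or during the intervention". Baseline comparability is to be checked with t-tests or Wilcoxon tests for continuous variables and chi-square tests for dichotomous ones. Neither stratification factor is named as a covariate. Sex enters only an exploratory model: "we will evaluate the interaction between sex and treatment group by using analyses of covariance". BMI stratum enters no stated model.

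**The concern.** Stratified allocation with balance inside the strata removes differences in sex and BMI group from the treatment comparison, so the estimate varies less from trial to trial. A model without those factors leaves their variation in the residual and reports a standard error that does not reflect this gain. The interval is then wider than it need be.

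The plan's covariate rule works against the design here. It admits a measure only when the arms differ on it, and stratification is there to prevent such a difference. The factors used to randomise are therefore those the rule is least likely to admit. At stake is some precision on the single primary endpoint, and a primary model whose covariates are fixed only after the data have been inspected.

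**Working it through.** **Inputs from the documents** (section D, sample size considerations): SD 6.1 and detectable difference 6.2 µmol/kg FFM/min, two-sided α 0.05, power 0.90, 22 completers and 28 enrolled per group, expected baseline Rd 44.5.

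**Assumed, because the documents do not say:** permuted blocks of 4 within the four sex-by-BMI strata, and the share R² of residual variance (after baseline Rd) that sex and BMI stratum explain, varied from 0 to 0.30.

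**1. The plan's sample size.** n = 2(1.960 + 1.282)² × (6.1/6.2)² = 20.3, so 21 per group by the normal approximation. The noncentral t gives power 0.895 at 21 and 0.909 at 22. So 22 per group reproduces; 22 + 6 = 28, and 6.2/44.5 = 13.9%. This calculation does not depend on the present point.

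**2. Does the covariate rule admit the factors?** With stratified blocks, the chi-square test flagged sex or BMI stratum in 0% of simulated trials. With 12 random drop-outs it flagged them in under 0.1%, and continuous BMI was flagged in about 0.4%. In practice the rule leaves the factors out.

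**3. Size under exact balance.** Without the factors, the reported SE is about 6.1 × √(2/22) = 1.84, while the true SD of the estimate is about 1.84 × √(1 − R²). The SE is therefore too large by a factor of 1/√(1 − R²), and the type I error is P(|t₄₁| > 2.020/√(1 − R²)). At R² = 0.05, 0.10, 0.20 and 0.30 the factor is 1.03, 1.05, 1.12 and 1.20, and the type I error is 4.5, 3.9, 2.9 and 2.0%.

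**4. Size with blocks of 4.** Incomplete blocks weaken the balance. Simulation of 44 completers, residual SD 6.1, 6,000 trials per cell (Monte Carlo error about 0.3 points on type I error):

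| R² | SE without / true SD | Type I error, without | Type I error, with | Power at 6.2, without | Power at 6.2, with |
|---|---|---|---|---|---|
| 0 | 1.85 / 1.84 | 4.8% | 4.9% | 90.0% | 89.9% |
| 0.05 | 1.85 / 1.82 | 4.7% | 5.1% | 90.7% | 91.3% |
| 0.10 | 1.86 / 1.76 | 3.6% | 4.6% | 91.8% | 93.2% |
| 0.20 | 1.86 / 1.69 | 3.1% | 5.1% | 91.9% | 94.8% |
| 0.30 | 1.86 / 1.60 | 2.4% | 5.2% | 92.8% | 97.2% |

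A separate run with 56 randomised and 12 random drop-outs gave type I error without the factors of 4.7, 5.2, 4.4, 3.8 and 2.5% in the same order, and power of about 90 to 92% without the factors and 90 to 97% with them.

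**5. No balance within strata.** Under unrestricted allocation, type I error without the factors stays at 4.7 to 5.2%, so there is no conservatism.

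**6. The other half of the covariate rule.** In a sketch with no treatment effect on Rd, treatment shifted another measure by 0.5 or 0.8 SD, and that measure correlated 0.3 or 0.5 with Rd. Following the rule gave type I error of 6.2 and 9.5% (correlation 0.3) and 7.9 and 20.2% (correlation 0.5).

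**The case against.** A reader might infer that the primary test simply is conservative and its standard error too wide. The documents do not support that as a statement of fact. It requires balance within strata, for which section C.3.3 gives no method, and prognostic value beyond baseline Rd, for which no figure is given.

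The share may well be small. Section D describes 6.1 as day-to-day variability, which stable traits do not explain, and baseline Rd already carries much of any sex or BMI effect. As an illustration, suppose true Rd is stable over follow-up with between-person variance V, measurement variance E, and strata explaining a share s of V. With λ = V/(V + E) and λ' = (1 − s)V/((1 − s)V + E), the residual share is 1 − (1 + λ')/(1 + λ). For between-person SD of 8 to 15 and s of 0.10 to 0.30, this is 0.4 to 3.8% if 6.1 is the SD of a difference (E = 6.1²/2 = 18.6), and 0.7 to 5.3% if it is the SD of one measurement (E = 37.2). Shares of 20 to 30% would need the strata to predict change over 16 weeks. Expressing Rd per kg of fat-free mass may also remove some sex and size variation. This objection stands as a limit on the likely size.

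The rodent data on sex concern response to NMN, not prognosis given baseline, and section D already plans an interaction model. That mostly stands too. A sex-dependent effect would, however, make sex predict post-treatment Rd. Assuming effects of 9.3 in women and 3.1 in men (mean 6.2), power was 0.87 without the strata and 0.88 with them. At the extreme of 12.4 and 0 it was 0.80 and 0.85.

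A reader might also infer that the omission undermines the planned power. It does not: without the factors, power at 6.2 is about 90% or slightly above across the assumed shares of 0 to 30%.

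**Conclusion.** The omission is real: the design stratifies on two factors, the primary model prespecifies neither, and the significance rule will almost never bring them in. The consequence is conditional. With balance within strata, the loss is negligible up to a 5% share of residual variance. At 10, 20 and 30% the model SE is about 6, 10 and 16% too large (1.86/1.76, 1.86/1.69, 1.86/1.60), and adding the factors would raise power at 6.2 by about 1, 3 and 4 points. These shares are assumptions, and the upper ones are hard to reconcile with an SD described as day-to-day variability.

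What is forgone is precision, not the stated 90% power. The test as written should not be called conservative overall, because the same sentence allows adjustment for measures that differ during treatment, and that can raise type I error above 5%. The change is worth making because it costs almost nothing and settles the primary model in advance.

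**What to change.** State the primary model in section D as post-treatment glucose Rd on treatment, baseline Rd, sex and BMI stratum (25.0 to 34.9 or 35.0 to 50.0 kg/m²), with strata as randomised. Let this replace the significance-based covariate rule, above all the part that admits measures differing during the intervention. Use the same terms, with the matching baseline value, for continuous secondary outcomes, and as the base of the exploratory sex-by-treatment model. State the block method in section C.3.3, in a form that does not compromise blinding, and bring the overview into line by naming BMI as well as sex.

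The cost is a few sentences and two residual degrees of freedom: 44 − 3 = 41 becomes 44 − 5 = 39, which moves the critical t from 2.020 to 2.023. If the factors explain nothing, power is essentially unchanged (90.0% against 89.9%). Sample size, conduct and data collection stay as they are.
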